- RV function (normal, mildly impaired, moderately impaired, severely impaired, peak tricuspid annular velocity, TAPSE, RVFAC) at 12 and 24 months
- Pulmonary artery pressure at 12 and 24 months
- RV volume at 12 and 24 months

Quality of Life

- SF-12
- KCCQ
- EQ-5D

Survival

- Perioperative mortality (greater in-hospital or 30-day mortality)
- Mortality

Serious Adverse Events

- Frequency of SAEs
- AV-Block requiring pacemaker implantation
- New-onset atrial fibrillation

Hospitalizations

- Index hospitalization LOS and ICU days
- All-cause readmissions and readmissions for heart failure and TR re-operation

Economic Outcomes

- Cost
- Cost-effectiveness

STUDY DESIGN

This is a multi-center randomized clinical trial. The trial will be conducted in highly experienced clinical centers participating in the NIH/CIHR supported Cardiothoracic Surgical Trials Network (CTSNet) and the Deutsches Zentrum für Herz- Kreislauf-Forschung (DZHK) supported German Society for Thoracic and Cardiovascular Surgery (DGTHG). The estimated enrollment period is 24 months (n = 400), and all patients will be followed for 60 months post-randomization. Endpoints will be measured at 30 days, 6, 12, 18, and 24 months. Survival will continue to be measured after the 24-month visit via vital sign checks at 36, 48 and 60 months.

RANDOMIZATION

Patients will be randomly assigned (1:1) to MVS + TV annuloplasty or MVS alone. Patient randomization will be stratified by TR severity and by clinical center. The randomization procedure will be performed intra-operatively, following **the placement of the TEE probe and after visualization and confirmation of cardiac anatomy eligibility**, in order to minimize the likelihood of enrolling patients in the study with

unexpected surgical contra-indications to TV repair. Randomization will be performed centrally through a Web-based data collection system that automates the delivery of the randomization assignments. The treatment assignment will be viewed by the site coordinator electronically, in a secure fashion, and electronic verification of the treatment assignment will be required before proceeding with the treatment intervention. From that point on, primary efficacy will be analyzed by intention-to-treat; that is, the patients will be grouped by their assignment at randomization whether or not they actually received the treatment to which they were assigned.

MASKING

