Economic Measures

Inpatient costs will be measured through the collection of hospital billing and resource utilization information. In addition to index hospitalization costs, costs associated with subsequent readmissions will also be included in the study. Patients will also be asked at each follow-up visit if they have been hospitalized at another hospital and if yes for how long.

For those institutions who participate in Vizient (formerly the University Healthsystems Consortium [UHC]), hospital costs and resource utilization data will be collected. Vizient works with academic medical centers around the country to collect and warehouse clinical, safety, operational and financial data. These data are used to compare performance among peer hospitals and identify best practice patterns. Participating centers will provide unique trial information and the dates of participation in the trial to Vizient who will provide a de-identified data set of the financial data for the trial to the investigators for analysis.

For institutions who do not participate in Vizient, hospital billing data from the UB-92 form will be collected in a de-identified manner from the institutional billing departments. As hospitalization practices differ substantially and detailed accounting data are unavailable for the participating Canadian and German centers, the cost and cost-effectiveness analysis will be restricted to US centers only.

Safety

Adverse Events

Please refer to the CTSN Clinical and Adverse Event Reporting and Adjudication Procedures guidance document for general reporting procedures and guidance on the determination of intervention-expected AEs.

Specific Adverse Event Definitions

AV Conduction Block leading to Permanent Pacemaker Placement

See “Cardiac Arrhythmias” below

New-onset Post-Operative Atrial Fibrillation

See “Cardiac Arrhythmias” below

Bleeding

A bleeding event is defined by any one of the following:

- Transfusion of > 5 units RBC within the first 24 hours following surgery
- Death due to hemorrhage
- Re-operation for hemorrhage or tamponade

NOTE: Hemorrhagic stroke is considered a neurological event and not as a separate bleeding event.

Cardiac Arrhythmias

Any documented arrhythmia that *results in clinical compromise* (e.g., hemodynamic compromise, oliguria, pre-syncope or syncope) that requires hospitalization or requires a physician visit or occurs during a hospital stay.

Cardiac arrhythmias are classified as follows:

- Cardiac arrest

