- Sustained ventricular arrhythmia requiring defibrillation or cardioversion.
- Sustained supraventricular arrhythmia requiring drug treatment or cardioversion (classified as either pre-existing or post-operative onset)
- Cardiac conduction abnormalities or sustained bradycardia requiring permanent pacemaker placement (includes all PPMs whether associated with a serious AE or not)

Pericardial Fluid Collection

Accumulation of fluid or clot in the pericardial space that requires surgical intervention or percutaneous catheter drainage. This event will be subdivided into those with clinical signs of tamponade (e.g., increased central venous pressure and decreased cardiac output) and those without signs of tamponade.

Pleural Effusion

Accumulation of fluid or clot in the pleural space documented by chest radiogram or chest CT that requires evacuation with surgical intervention, chest tube or pigtail placement or medical management such as diuresis.

Pneumothorax

Presence of gas in the pleural space, documented by chest radiogram or chest CT, which requires evacuation or prolongs the duration of chest tube drainage.

Hepatic Dysfunction

Liver injury **and** impaired liver function defined as:

- ALT \geq 3xURL *and* total bilirubin* \geq 2xURL (>35% direct), **or**
- ALT \geq 3xURL *and* INR** $>$ 1.5.

* Serum bilirubin fractionation should be performed if testing is available; if unavailable, measure urinary bilirubin via dipstick. If fractionation is unavailable and ALT \geq 3xURL and total bilirubin \geq 2xURL, then the event is still to be reported as an SAE.

** INR testing not required per protocol and the threshold value does not apply to subjects receiving anticoagulants. If INR measurement is obtained, the value is to be recorded on the SAE form.

Major Infection

A new clinical infection accompanied by pain, fever, drainage and/or leukocytosis that is treated by anti-microbial agents (non-prophylactic). A positive culture from the infected site or organ should be present unless strong clinical evidence indicates the need for treatment despite negative cultures. The general categories of infection are listed below:

Localized Infection

Infection localized to any organ system or region (e.g., mediastinitis) without evidence of systemic involvement (see “*sepsis*” below), ascertained by standard clinical methods and either associated with evidence of bacterial, viral, fungal or protozoal infection, and/or requiring empirical treatment.

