5.2.5 Serious Adverse Events

- Frequency of SAEs
- AV-Block requiring pacemaker implantation
- New-onset atrial fibrillation

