6.5.2.5 Serious Adverse Events

Differences in the rate of individual serious AEs, AV-Block requiring pacemaker implantation, and new-onset atrial fibrillation within 24 months post-randomization will be compared between randomization groups using Poisson regression. Ninety-five percent confidence intervals for the rate ratios for individual AEs for treatment with MVS and TV annuloplasty versus MVS alone will be computed.

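### New-onset AF and AV-block pacemaker are defined only by reference to an arrhythmia definition that omits treated AF without clinical compromise and does not separate AV block from other pacemaker indications

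*Protocol*

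**What the plan says.** The protocol (Endpoints, Serious Adverse Events) and SAP 5.2.5 list two specific events beside the overall frequency of serious adverse events: "AV-Block requiring pacemaker implantation" and "New-onset atrial fibrillation". SAP 6.5.2.5 states that "AV-Block requiring pacemaker implantation, and new-onset atrial fibrillation within 24 months post-randomization will be compared between randomization groups", by Poisson regression.

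Under Specific Adverse Event Definitions, the protocol has an entry headed "AV Conduction Block leading to Permanent Pacemaker Placement" and another headed "New-onset Post-Operative Atrial Fibrillation". Neither contains a definition; each sends the reader to Cardiac Arrhythmias. That entry covers "Any documented arrhythmia that *results in clinical compromise* (e.g., hemodynamic compromise, oliguria, pre-syncope or syncope" among its examples, and adds that the event must lead to hospitalization or a physician visit, or occur in hospital. Four classes follow. Two matter here:

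- supraventricular: "Sustained supraventricular arrhythmia requiring drug treatment or cardioversion (classified as either pre-existing or post-operative onset";
- pacemaker: "Cardiac conduction abnormalities or sustained bradycardia requiring permanent pacemaker placement (includes all PPMs whether associated with a serious AE or not".

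The SAP adds no event definition. The network's adverse event guidance, which is not among the documents, is cited for reporting procedures and for deciding which events are expected, not for defining events.

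**The concern.** The endpoint names and the counting rule do not match. For AF the rule is narrower than the name, because of the compromise condition, and also broader, because the class does not name AF. For AV block the rule is broader than the name.

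The AF gap arises at reporting. A site that reads the opening sentence will not submit treated AF without compromise as an event of this type; a site that reads only the class line will. The protocol allows up to 50 centers, so practice may differ between them. Investigators know the treatment assignment and make the first call on whether there was compromise. The Event Adjudication Committee reviews what is reported and cannot be relied on to recover what was not.

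At stake is how two safety comparisons between annuloplasty and no annuloplasty should be read. A published rate labelled new-onset AF would be understood as all such AF. A published AV-block pacemaker ratio would be understood as specific to AV block.

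**Working it through.** No stated figure needs reproducing: the documents give no expected rate or power for either endpoint. The check is first textual.

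| Event | Opening compromise condition | Class | Counted as written? |
|---|---|---|---|
| New sustained AF, treated, with compromise, in hospital | Met | Supraventricular, post-operative onset | Yes |
| Same, without compromise | Not met, no waiver | Fits the class line only | No |
| Another sustained, treated supraventricular arrhythmia with compromise | Met | Same class as AF | Yes, not separated from AF |
| AV block with permanent pacemaker, no compromise | Apparently waived by the parenthesis | Pacemaker | Yes |
| Sustained bradycardia of other cause, with permanent pacemaker | Apparently waived | Pacemaker | Yes, not separated from AV block |
| Bradycardia without permanent pacemaker | – | None in this class | No |

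The waiver in the pacemaker class supports the literal reading of the AF rule: the authors wrote an exception where they wanted one, and wrote none for supraventricular arrhythmia.

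**AF, effect on precision.** Take one event per patient and equal follow-up. With expected event counts E0 and E1, the approximate standard error of the log rate ratio is √(1/E0 + 1/E1). If a share f of episodes is counted, the same in both arms, the expected ratio is unchanged and the standard error is multiplied by 1/√f: 1/√0.5 = 1.41 and 1/√0.25 = 2. If the share differs between arms, the ratio itself is multiplied by f1/f0.

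An illustration on assumed rates (MVS alone 30%, annuloplasty 45%, 200 per arm, two-sided 0.05):

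- All counted: E = 60 and 90; SE = √(1/60 + 1/90) = 0.167; ln 1.5 = 0.405; z = 2.43; power = Φ(2.43 − 1.96), about 68%.
- 40% counted: E = 24 and 36; SE = 0.264; z = 1.54; power about 34%.
- 20% counted: E = 12 and 18; SE = 0.373; z = 1.09; power about 19%.

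If only 130 per arm are free of AF at baseline (also assumed), the three figures are about 50%, 24% and 14%.

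**Pacemaker, effect on the ratio.** Let p be the AV-block pacemaker rate with MVS alone, 3 the assumed true ratio, and b the rate of other pacemakers in each arm. The observed ratio is (3p + b)/(p + b).

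| | b = 1% | b = 2% | b = 4% |
|---|---|---|---|
| p = 2% | 7/3 = 2.33 | 8/4 = 2.00 | 10/6 = 1.67 |
| p = 4% | 13/5 = 2.60 | 14/6 = 2.33 | 16/8 = 2.00 |

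The absolute difference stays at 2p (4 or 8 percentage points) throughout.

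**The case against.** The compromise condition may be deliberate. Both endpoints stand under a serious adverse event heading, and the revision history records that the arrhythmia definition was clarified for consistency between centers. Counting all treated AF is then a different endpoint. This has force, but the heading does not settle the matter: SAP 6.5.2.5 lists the two endpoints alongside the individual serious events, and the pacemaker class expressly admits non-serious ones. If the restriction is intended, the endpoint name should say so.

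The separate entry headings could be read as limiting each class to the named rhythm or indication, so that other supraventricular arrhythmias are not AF and sinus-node pacemakers are not AV block. That reading is possible and would answer the pooling points, but no rule in either document states it, and it does not remove the compromise condition. Case report forms, which are not supplied, may record rhythm and indication.

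The new-onset element is partly handled. The supraventricular class records pre-existing versus post-operative onset, the baseline medical history includes arrhythmias, and SAP 6.1 counts patient-time at risk for the specific event. The SAP does not say whether a patient with prior AF is at risk.

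A reader might infer more than the documents support:

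- That any bradycardia counts towards AV block. It does not; a permanent pacemaker is required, and the class contains the named endpoint.
- That these are the only specific adverse events among the secondary endpoints. Stroke and serious heart failure events also enter, through MACCE.
- That they are the main harms of annuloplasty. The documents do not rank harms.
- That reporting rests on site judgment alone. An adjudication committee unaffiliated with trial conduct reviews all adverse events, although its masking is not stated.
- That a well-powered AF comparison is being lost. No power is claimed for it. A two-proportion test on the rates assumed above would give 88%, 39% and 21%, but the planned method is Poisson regression, and the rates have no source in the documents.

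**Conclusion.** The point holds for both endpoints, more strongly for AF. As written, the plan undercounts new-onset AF by excluding treated episodes without clinical compromise, and does not separate AF from other supraventricular arrhythmias. For AV block nothing is missed where a permanent pacemaker is placed, but the ratio is diluted by pacemakers placed for other reasons; if those are equally frequent in both arms, the absolute excess is not.

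The size is not known. It depends on the share of AF episodes with compromise, on whether that share is judged alike in both arms, and on the mix of pacemaker indications; the documents give none of these. The calculations show direction and mechanism under stated assumptions only. The AF conclusion rests on a literal reading of the opening sentence, which the waiver in the pacemaker class supports. Only secondary safety endpoints are affected. The definitions should be corrected, but the trial's main conclusion does not depend on them.

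**What to change.** Give each endpoint its own definition in the protocol and carry the same wording into SAP 5.2.5 and 6.5.2.5.

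- New-onset AF: documented sustained AF or flutter after surgery that requires drug treatment or cardioversion, regardless of clinical compromise. Analyse it by randomized group among patients with no AF in the baseline medical history. Report AF with compromise separately if that is wanted.
- Pacemaker: keep counting every permanent pacemaker, record the indication (AV block, sinus-node dysfunction, other), and report AV-block pacemakers and all permanent pacemakers as separate lines.

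The cost is definition wording, one indication field and more non-serious AF reports. Baseline arrhythmia history is already collected and adjudication is already in place. The SAP's COVID-19 section shows that two-year visits were already being planned for when it was written, so events from earlier follow-up may have been reported under the current wording. Where they cannot be recovered from source records, the fallback is to rename the endpoints to what was counted: supraventricular arrhythmia with clinical compromise, and permanent pacemaker for any indication.

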In patients with severe TR already undergoing surgery for left valvular pathology, surgical correction is recommended by the AHA/ACC and ESC guidelines (Nishimura, Otto et al. 2014). Significant equipoise exists, however, as to the optimal approach for patients with only moderate TR or mild TR with annular dilation. Some centers argue that performing a TV annuloplasty at the time of MVS influences the incidence of right heart failure and improves long term survival, yet others believe the risk of an additional surgical procedure outweighs the potential benefit (Yilmaz, Suri et al. 2011). According to the STS database, among 46,500 isolated primary MV operations performed between 2011 and 2014, TV repair was performed in 4% of patients with none or mild TR, 35% of patients with moderate TR, and 79% of patients with severe TR. These practice patterns serve to reflect an uncertainty of benefit of concomitant TV repair for moderate TR as well as variability in practice.

Establishing whether or not definitive benefit is conferred by performing TV repair at the time of MVS for degenerative MV disease should provide the level of evidence needed to provide rigorous recommendations for the management of this significant patient population. As such, the Network has designed a trial to evaluate the efficacy and safety of concomitant TR annuloplasty at the time of MVS.

Justification of Primary Endpoint Selection

Ideally, the effectiveness of TR repair should be measured by the degree to which it reduces relevant clinical events. However, the combination of the relatively low expected two-year event rate in the target population of degenerative MR with moderate or less TR, and logistical constraints on the sample size for the trial, precludes using an endpoint defined in terms of clinical events alone. Instead, we propose a composite endpoint of death from any cause, progression of TR (measured echocardiographically)

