We propose considering increasing sample size should the observed primary endpoint event rate among patients randomized to no repair of the TV be appreciably less than the assumed rate of 25%. The planned sample size of 400 patients has been determined to ensure that power is at least 90% to detect a 52% relative reduction of “failure” for patients randomized to tricuspid repair compared to no repair. Should the “failure” rate among controls be 20%, 400 patients provides approximately 83% power to detect a 52% relative reduction; for a 15% “failure” rate among controls there is approximately 70% power to detect a 52% relative reduction. Therefore, we suggest that the primary endpoint event rate be examined in control patients, using the same analysis set to be used for the interim analysis, and that the sample size be increased by up to 100 additional patients in order to maintain 80% power under the original alternative hypothesis for control rates as low as 15%. If no interim analysis is conducted or accrual is complete at the time of the first interim analysis, the sample size re-estimation will not be considered.

Assessment of Balance of the Randomization

The success of the randomization procedure in balancing important covariates between randomization groups will be assessed at the interim analysis and at the final analysis. Continuous measures will be compared using t-tests, while chi-squared tests will be used to compare categorical variables. As 400 patients will be randomized, no substantial imbalances are expected. However, should any covariate differ significantly between treatment groups at the 0.01 level, and be substantively large, we will adjust for those covariates in a secondary analysis of the primary endpoint.

Additional analysis of the primary endpoint

A subgroup analysis of the primary endpoint will be performed with subgroups defined by whether or not patients received a CABG procedure during the initial surgery. This analysis will be performed in the same manner as that described for the primary analysis.

Analyses of Secondary Endpoints

Individual components of the primary endpoint

Mortality: Differences in the rate of mortality between randomization groups over the first 24 months and the planned 60 months of follow-up will be assessed using Cox proportional hazards regression.

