6.5.2 Analyses of Secondary Clinical Endpoints

6.5.2.1 Clinical and Functional Outcomes

MACCE: The rate of major cerebrovascular or cardiac events (defined as the

composite event of death, stroke, and serious heart failure events) will be compared between randomization groups over 24 months post-randomization using a Cox proportional hazards regression model.

Reoperation for TR: The difference in the rate of requiring subsequent TV annuloplasty after the initial MVS will be compared between randomization groups over 24 months post-randomization. Reoperation for TR may not occur because death from any cause precedes the event; thus, it is possible that censoring patients at all-cause mortality will lead to biased estimates when analyzing time to first event. Therefore, competing risks analysis using the methods of Fine and Gray (Fine & Gray, 1999) will be used to estimate group differences.

NYHA: The distribution of NYHA at 30 days, 6, 12 and 24 months will be presented for each randomization arm and compared using chi-squared tests.

Diuretic Use: The distribution of diuretic use at 30 days, 6, 12 and 24 months will be presented for each randomization arm and compared using chi-squared tests.

Six Minute Walk: Differences between groups in the distances travelled during the 6MWT at 30 days, 6, 12 and 24 months will be compared using Wilcoxon Rank-Sum tests.

Gait Speed Tests: Differences between groups in gait speed at 12 and 24 months will be compared using Wilcoxon Rank-Sum tests.

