6.5.2.4 Survival

Perioperative Mortality: The distribution of vital status at 30 days post-surgery will be presented for each randomization arm and compared using chi-squared tests.

Mortality at 2 and 5 years post-randomization: Differences in the rate of mortality between randomization groups over the first 24 months and the planned 60 months of post-randomization follow-up will be assessed using Cox proportional hazards regression.

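### The Cox comparisons of mortality and MACCE name no TR-severity stratum, and the hazard ratio is the only planned between-arm measure of mortality beyond 30 days

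*Protocol*

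**What the plan says.** **Mortality.** The protocol (Analytical Plan, Analyses of Secondary Endpoints, Mortality) states that group differences "over the first 24 months and the planned 60 months of follow-up will be assessed using Cox proportional hazards regression". SAP 6.5.2.4 carries this forward: mortality over the two periods of "post-randomization follow-up will be assessed using Cox proportional hazards regression".

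**MACCE.** SAP 6.5.2.1 compares the composite "between randomization groups over 24 months post-randomization using a Cox proportional hazards regression model".

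**Covariates.** None of these descriptions names a covariate or stratum. The protocol (Randomization Design and Procedure) stratifies allocation by center and by whether TR is moderate. The primary log-binomial model (SAP 6.5.1.2) includes the TR-severity indicator and explains why center is left out.

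**Other mortality analyses.** SAP 6.5.2.4 compares 30-day vital status by chi-squared test. SAP 6.1 plans Kaplan-Meier summaries of time-to-event variables and has a general clause allowing another technique if a planned one turns out unsuitable. Neither document names a proportional-hazards check, a survival difference at a fixed time, or a restricted mean survival time (RMST).

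**The concern.** There are two gaps.

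First, the stratification factor. The primary analysis respects TR severity, while the Cox comparisons as described do not mention it. An analyst could fit them with or without it, and the two fits estimate slightly different hazard ratios with slightly different standard errors. That choice should not be open once outcomes are visible.

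Second, the summary measure. The protocol's Rationale for the Trial reports that some centers hold that annuloplasty "influences the incidence of right heart failure and improves long term survival". It also reports the opposing opinion, that the added operation costs more in risk than it may gain. Also, "The randomization procedure will be performed intra-operatively", so any procedural deaths fall at the very start of the Cox time scale. If both views were partly right, the hazard ratio would be above 1 early and below 1 later. A single Cox ratio then averages the two periods with weights that depend on how long patients are followed. The 24- and 60-month ratios would differ for that reason alone, and no absolute comparison with an interval is planned to help a reader interpret them. The Kaplan-Meier summaries are descriptive, and the fallback clause names neither a trigger nor an alternative for Cox.

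**Working it through.** **Figures in the plan.** The documents give no mortality rate, hazard ratio, event count or power for mortality, so there is nothing to reproduce on this point. All rates below are assumptions. From the documents: 400 patients, 1:1 (200 per arm), horizons of 24 and 60 months.

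**Model.** Constant hazard in month 1, another constant hazard afterwards, no censoring before the horizon.

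Lead example: 30-day mortality 1.5% (MVS alone) and 3.0% (repair), then hazards of 0.03 and 0.02 per year.

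- Month-1 hazard ratio: ln(0.970)/ln(0.985) = 0.03046/0.01511 = 2.02
- Later hazard ratio: 0.02/0.03 = 0.67

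**Survival at the horizon**, S(T) = (1 − 30-day risk) × exp(−hazard × (T − 1/12)):

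- 24 months: MVS alone 0.985 × exp(−0.0575) = 93.00%; repair 0.970 × exp(−0.0383) = 93.35%
- 60 months: MVS alone 0.985 × exp(−0.1475) = 84.99%; repair 0.970 × exp(−0.0983) = 87.92%

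**Limiting Cox ratio.** Solve for β: ∫[S1λ1 − w(S1λ1 + S0λ0)]dt = 0, with w = e^β S1/(e^β S1 + S0). This gives 0.955 at 24 months and 0.800 at 60 months. As a hand check, the ratio of cumulative hazards is 0.0688/0.0726 = 0.947 and 0.1288/0.1626 = 0.792. Reading 3% and 2% as annual risks instead of hazards gives 0.949 and 0.796.

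**RMST difference** (integral of S1 − S0).

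| 30-day risk, MVS alone v repair | Horizon | Cox ratio | Survival difference (repair − MVS alone) | RMST difference |
|---|---|---|---|---|
| 1.5% v 3.0% | 24 mo | 0.955 | +0.36 points | −4.1 days |
| | 60 mo | 0.800 | +2.92 points | +14.2 days |
| 1% v 2% | 24 mo | 0.872 | +0.85 points | −0.6 days |
| | 60 mo | 0.758 | +3.40 points | +23.0 days |
| 1% v 3% | 24 mo | 1.029 | −0.12 points | −7.6 days |
| | 60 mo | 0.828 | +2.49 points | +5.8 days |

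In all six rows the ratio and the survival difference agree in direction. The ratio moves with the horizon in every example.

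**Wider range.** The same calculation was run over 320 assumed scenarios: control 30-day mortality 0.5–3%, excess with repair 0.5–3 points, later control mortality 1–5% per year, late hazard ratio 0.5–0.9. The Cox ratio contradicted survival at its own horizon in 0. It disagreed in sign with RMST in 72 (24 months) and 64 (60 months). It moved from above 1 at 24 months to below 1 at 60 months in 92.

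**Precision, lead example, 200 per arm.**

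- Expected deaths: 200 × 7.00% = 14.0 and 200 × 6.65% = 13.3 by 24 months; 30.0 and 24.2 by 60 months
- Cox ratio at 24 months: SE of log ratio ≈ √(1/14.0 + 1/13.3) = 0.38, 95% CI about 0.45 to 2.0
- Survival difference at 24 months: SE √[(0.930 × 0.070 + 0.9335 × 0.0665)/200] = 2.5 points, 95% CI about −4.6 to +5.3 points; at 60 months SE 3.4 points, about −3.8 to +9.6
- RMST difference: SE about 13 days at 24 months (95% CI about −30 to +22) and 42 days at 60 months (about −69 to +97)
- Deaths in the first 30 days: 200 × 1.5% = 3 and 200 × 3.0% = 6

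**TR-severity stratum.** Its effect cannot be sized, because the documents give no mortality or MACCE rate by TR severity.

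**The case against.** A reader might infer that the Cox ratio can point the wrong way. The calculations do not support that for survival: at each horizon the ratio agreed with which arm had more patients alive. It disagrees only with RMST, or with the hazard in one period taken alone. To call that wrong is to decide beforehand that RMST is the right measure. The disagreement in the lead example is also about 4 days with a standard error of about 13.

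A reader might also infer that early risk against late survival is what the trial set out to test. The primary aim is a two-year composite. The rationale reports two rival opinions, and it speaks of procedural risk, not operative death. Mortality is a secondary endpoint with no stated power: with 40 deaths, power for a hazard ratio of 0.7 is Φ(√(40/4) × 0.357 − 1.96), about 20%.

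The plan is not blind to timing either. Perioperative mortality is a separate endpoint with its own 30-day comparison, Cox is fitted at two horizons, and Kaplan-Meier summaries are planned. A separate 30-day hazard ratio would rest on about 3 against 6 deaths and add little to that comparison. For MACCE, no crossing of hazards has been shown. And silence about covariates in a one-sentence method is not a decision to leave them out.

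All of this stands. It rules out replacing Cox, and it limits the MACCE point to the stratum. It does not supply the missing specification: the stratum is still unnamed, and mortality beyond 30 days still has no planned between-arm measure other than the ratio.

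**Conclusion.** The point holds as a modest gap in pre-specification. The Cox descriptions for mortality and MACCE do not name the TR-severity stratum used in randomization and in the primary model. The hazard ratio is also the only planned between-arm measure of mortality beyond 30 days. If the two effects raised in the rationale were both present, the ratio would depend on follow-up: about 0.95 at 24 months and 0.80 at 60 months in the lead example, and 0.87 to 1.03 and 0.76 to 0.83 across the three examples. These figures rest wholly on assumed mortality rates and a two-period hazard. The documents do not support the stronger conclusions that the ratio misstates which arm survives better, or that Cox should give way to RMST. What is at stake is how readable and how firmly fixed an unpowered secondary comparison is; the primary result is not affected.

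**What to change.** In the protocol's mortality paragraph and SAP 6.5.2.4, keep the Cox model and state that it is stratified by baseline TR severity (moderate or less than moderate). Alongside it, pre-specify the between-arm difference in Kaplan-Meier survival with 95% CI at 24 and at 60 months, and the RMST difference with 95% CI at the same horizons as supportive. Present these as estimates, with no added significance tests. In SAP 6.5.2.1, state the same stratification for the MACCE Cox model.

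The SAP allows revision before data lock, no new data are needed, and the cost is a few sentences and a little code. The downside is slightly more analysis work and wide intervals because deaths are few: about ±5 points at 24 months and ±7 points at 60 months in the lead example.
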